Protocol Overview	
 1. Informed consent will be obtained. 2. Study eligibility will be assessed. 3. Prior to randomization, the participant's willingness to proceed into the randomized trial will be confirmed. 4. Eligible eyes (one per participant) will be randomly assigned to photobiomodulation or sham. If a participant has two eligible eyes, the eye with the greatest CST will be selected as the study eye and the non-study eye will be followed to evaluate any potential contralateral effect. 5. Training for at-home use will be performed with the randomized device on the day of randomization. 6. A follow-up phone call is performed at 1 week. 7. Participants will return for a follow-up visit every month for the first ~4 months and then every 2 months for 4 months after the primary outcome. The primary outcome assessment will be at ~4 months. 8. Following the primary outcome assessment, participants in the active group will end device use and participants in the sham group will be given the option to switch to the active treatment for the next 4 months. Participants in both groups who do not continue treatment will be given the option to end study participation after the primary outcome visit. A summary of treatment procedures is included below.

SCHEMATIC OF STUDY DESIGN

SCHEDULE OF STUDY VISITS AND PROCEDURES

	Baseline	1-week Phone Call	Interim Visits (1, 2, 3, 6M)	Primary Outcome and Final Visits	DME Tx Initiation Visit*
Device Training	X				
Randomization	X				
E-ETDRS Best Corrected Visual Acuity [†]	X		X	X	X [‡]
Spectral Domain OCT [§]	X		X	X	X
OCTA [¶]	X			X	
Eye Exam [¶]	X		If Needed	X	X
Blood Pressure	X				
HbA1c ^{**}	X				
Compliance Assessment		X	X	X	

Notes

Testing is only required for the study eye unless otherwise specified below.

*Alternative DME treatment (e.g. anti-VEGF) should not be performed unless protocol criteria are met. If alternative DME treatment is planned at an unscheduled visit, study testing must be completed prior to treatment.

[†]Visual acuity performed on both eyes at each visit, including protocol refraction on both eyes at baseline, 4-month, and final visit, and on the study eye only at all other protocol visits.

[‡]Usual care vision may be used if eye has already been dilated when treatment is planned.

[§]OCT in both eyes at all visits; OCT may be obtained with Zeiss Cirrus or Heidelberg Spectralis OCT machines only.

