405 Individuals who do not initially meet study eligibility requirements may be rescreened at a later
406 date per investigator discretion.

407 All testing does not need to be completed on the same day provided it is within the windows
408 specified below.

409 **2.3.2 Screening Procedures**

410 The following procedures are needed to confirm eligibility and/or serve as baseline measures for
411 the randomized trial:

412 • If a procedure has been performed using the study technique and by study certified
413 personnel as part of usual care, then it does not need to be repeated specifically for the
414 study if it was performed within the defined time windows specified below.

415 • The testing procedures are detailed in the DRCR Retina Network procedures manuals.
416 Visual acuity testing, ocular exam, and OCT will be performed by DRCR Retina Network
417 certified personnel.

418 • OCTs meeting DRCR Retina Network criteria for manual grading will be sent to a reading
419 center, but study participant eligibility is determined by the site (i.e., individuals deemed
420 eligible by the investigator will be randomized without pre-randomization reading center
421 confirmation).

422 1. Self-reported demographics (date of birth, sex, race and ethnicity)

423 2. Medical history (pre-existing medical conditions, concomitant medications, as well as ocular
424 diseases, surgeries, and treatment)

425 ➤ Medical history will be obtained by medical charts if available at the enrolling site;
426 otherwise, it will be self-reported

427 3. Electronic-ETDRS visual acuity testing at 3 meters using the Electronic Visual Acuity Tester
428 (including protocol refraction) in study eye only (*within prior 14 days of randomization*).

429 4. Spectral-Domain OCT using Zeiss Cirrus or Heidelberg Spectralis in both eyes (*within prior
430 14 days of randomization*).

431 5. Ocular examination on each eye including slit lamp, measurement of intraocular pressure, lens
432 assessment, and dilated ophthalmoscopy (*within prior 14 days of randomization*).

433 6. OCT angiography on the study eye (*within prior 14 days of randomization*).

434 ➤ Only obtained by a subset of sites with OCT angiography capabilities.

435 7. Measurement of blood pressure.

436 8. Laboratory Testing- HbA1c.

437 • *HbA1c does not need to be repeated if available in the prior 3 months. If not available at*
438 *the time of randomization, the individual may be enrolled but the test must be obtained*

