 513 (because of unforeseen circumstances) are unable or unwilling to return for all follow-up visits
 514 will be permitted to return for key visits only as an alternative to withdrawal from the study.
 515 Participants who are not using a device during the post-outcome phase but have not received
 516 alternative treatment will be given the option to continue study visits or end study participation
 517 early.

518

519 Additional phone contacts may be performed as needed.

520 **3.2.1 Text Message Reminders**

521 For participants randomly assigned to text message reminders, periodic messages will be sent by
 522 the Coordinating Center with a reminder to comply with the study device schedule.

523 **3.3 Procedures at Study Visits**

524 The following procedures will be performed in both groups at each visit, unless otherwise
 525 specified:

- 526 1. E-ETDRS visual acuity testing (best corrected) in each eye.
 - 527 • A protocol refraction in the study eye is required at each visit. Refraction in the non-study
 528 eye is only required at the 4 and 8 month visits. When a refraction is not performed, the
 529 most recently performed refraction is used for the testing.
- 530 2. Spectral-Domain OCT using Zeiss Cirrus or Heidelberg Spectralis in both eyes
 - 531 • The same machine type (Cirrus or Spectralis) used at baseline should be used during
 532 follow-up.
- 533 3. Ocular exam in the study eye, including slit lamp examination with lens assessment,
 534 measurement of intraocular pressure, and dilated ophthalmoscopy.
 - 535 • Required at Primary Outcome and 4-Month Post Outcome visits only. Otherwise,
 536 ocular exam is at investigator discretion. In general, an ocular exam should be
 537 completed if the OCT and/or visual acuity have worsened since baseline (e.g. more
 538 than 10% increase in CSF thickness or 5 letter loss in VA).

539 4. OCT angiography on the study eye if obtained at baseline (4 month/primary outcome visit
540 only)

- 541 • Only obtained by a subset of sites with OCT angiography capabilities.
- 542 • *See procedure manual for more details on acquisition, including which fields to collect*
543 *on a given OCT angiography system.*

544 5. Compliance assessment

- 545 • The site personnel will download the compliance data and re-emphasize the importance
546 of compliance with device use

547 All of the testing procedures do not need to be performed on the same day, provided that they are

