1070 as mandated by NIH guidelines. Subgroup factors will be analyzed as continuous/ordinal variables
1071 where possible.

1072 **7.18 Multiple Comparisons/Multiplicity**

1073 Due to the large number of outcomes evaluated, only $P < .05$ will be considered of interest and
1074 warranting further exploration. It is recognized that this does not completely control the Type I
1075 error rate. There will be no other adjustments made for multiple comparisons or multiple testing.

1076 **7.19 Additional Tabulations and Analyses**

1077 To evaluate the potential contralateral effect, visual acuity, OCT measurements, and treatment for
1078 DME in non-study eyes will be tabulated at primary outcome visit by the treatment group assigned
1079 to the study eye. These outcomes will be analyzed and presented similarly to the primary and
1080 secondary analyses as specified above for the study eyes, with the exception that no imputation
1081 will be performed for missing data.

1082 This pilot study is being conducted to determine whether the conduct of a pivotal trial has merit
1083 based on an anatomic outcome and to provide information on outcome measures needed to design
1084 a pivotal trial. If the results of this study support proceeding with a pivotal trial after evaluation of
1085 all the data and discussion within DRCR, information from this study will contribute to designing
1086 the pivotal trial. The standard deviation of the difference in visual acuity will be used in the sample
1087 size calculation of the pivotal trial. Patient compliance (for example, the proportion of enrolled
1088 participants that are randomized and the proportion of randomized participants who comply with
1089 the use of the study device post-randomization) will also aid in the design of the pivotal trial.

1090 **CHAPTER 8: DATA COLLECTION AND MONITORING**

1091 **8.1 Case Report Forms and Device Data**

1092 The main study data are collected through electronic case report forms (CRFs). Compliance data
1093 are collected via electronic device data files obtained from the study device. When data are directly
1094 collected in electronic case report forms, this will be considered the source data. Each participating
1095 site will maintain appropriate medical and research records for this trial, in compliance with ICH
1096 E6 and regulatory and institutional requirements for the protection of confidentiality of
1097 participants.

1098 **8.2 Study Records Retention**

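### Protocol 2.3.2 limits baseline acuity and refraction to the study eye, contradicting the visit schedule and leaving the contralateral acuity-change analysis without a secure baseline

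*Protocol*

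**What the plan says.** Protocol 2.3.2 introduces its list with "The following procedures are needed to confirm eligibility and/or serve as baseline measures for" the randomized trial. Item 3 is E-ETDRS acuity, qualified as "including protocol refraction) in study eye only". The next two items, OCT and ocular examination, cover both eyes.

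The notes to the Schedule of Study Visits and Procedures begin with a default, "Testing is only required for the study eye unless otherwise specified below", and then depart from it for acuity: "Visual acuity performed on both eyes at each visit, including protocol refraction on both eyes at baseline, 4-month, and final visit".

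For follow-up visits, Protocol 3.3 asks for "E-ETDRS visual acuity testing (best corrected) in each eye". It adds that refraction in the non-study "eye is only required at the 4 and 8 month visits. When a refraction is not performed, the" "most recently performed refraction is used for the testing".

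Protocol 7.19 sets out the contralateral analysis: "To evaluate the potential contralateral effect, visual acuity, OCT measurements, and treatment for" DME in non-study eyes are tabulated at the primary outcome visit by the study eye's assigned group. They are then analysed along the lines of the study-eye primary and secondary analyses, with no imputation. SAP 6.0 repeats this. It adds that if the study eye is treated for DR or DME, the last non-study-eye measurement before that treatment is used.

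**The concern.** Two current parts of the protocol give different instructions on which eye has its acuity and refraction measured at baseline. A baseline measurement that is not taken cannot be recovered later.

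What is at stake is the acuity part of the contralateral analysis. The study-eye acuity analyses that it is meant to mirror are built on a baseline score. If the non-study eye has none, the mirrored analysis cannot be done for that participant. If it has a score taken without protocol refraction, the later refracted score is not measured on the same footing.

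**Working it through.** No arithmetic applies; the check is a comparison of texts.

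1. **Baseline instruction.** Protocol 2.3.2 item 3 says study eye only. The schedule footnote says both eyes, for acuity and for refraction. The schedule's study-eye default does not reconcile them, because it yields to any footnote that says otherwise, and the acuity footnote does.

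2. **Does a narrower reading of 2.3.2 remove the conflict?** There are two readings.
   - *Reading A: the limit covers acuity and refraction.* The non-study eye has no baseline score. This contradicts the footnote on both counts.
   - *Reading B: the limit covers refraction only.* A baseline score may exist, but without protocol refraction. This still contradicts the footnote, which names refraction in both eyes at baseline.

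   The conflict stands either way.

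3. **Does Protocol 3.3 settle it?** No. It governs follow-up visits, so its naming of only the 4- and 8-month visits for non-study-eye refraction says nothing about baseline. It does assume that an earlier refraction exists to be reused. Under either reading there may be no protocol refraction to reuse at months 1 to 3. Those interim scores matter only where SAP 6.0 carries one forward because the study eye was treated.

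4. **What the contralateral analysis needs.** The study-eye models in Protocol 7.8 and SAP 2.2 are:
   - loss of 5 or more letters from baseline, by logistic regression with baseline acuity as a covariate;
   - mean acuity change, which Protocol 7.8 only describes and SAP 2.2 compares by ANCOVA adjusted for baseline acuity.

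   Applied to the non-study eye, both outcomes and the covariate are undefined under Reading A. Under Reading B they can be computed, but a refracted month-4 score is set against an unrefracted baseline.

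5. **What it does not need.** Baseline OCT is taken in both eyes under 2.3.2 and under the schedule, so contralateral CST and retinal volume are unaffected. DME treatment of the non-study eye needs no baseline acuity. Month-4 non-study-eye acuity can be tabulated by arm without a baseline.

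**The case against.** The strongest reply is that the protocol already contains the requirement: the footnote expressly overrides the study-eye default, and nothing makes 2.3.2 the governing list. Sites are also referred to procedure manuals that are not among the documents. This stands as a limit on the likely effect, but it does not remove the contradiction.

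A second reply comes from Protocol 2.2.2. Where two eyes are eligible, the thicker one becomes the study eye. Establishing that both are eligible requires a best-corrected score of at least 79 in each, so those participants should have fellow-eye acuity anyway. This too stands, and it narrows the gap. It does not close it, because Protocol 7.19 refers to non-study eyes generally, and 2.2.3 sets no eligibility criteria for them.

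A reader might infer more than the documents support:

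- *That all non-study-eye baseline acuity is missing at the sites concerned.* This only restates the premise that a site follows 2.3.2 and ignores the schedule. The documents do not show that any did.
- *That affected participants leave the contralateral analysis altogether, or that its acuity question cannot be answered.* The OCT and treatment outcomes remain, and month-4 acuity can still be tabulated by arm.
- *That a first refraction at 4 months produces a spurious gain on top of the missing baselines.* The two harms belong to different readings: with no baseline score there is no gain to compute, and with one the score is not missing. Nor do the documents point to bias between arms. The baseline test precedes randomization, which is stratified by site, and Protocol 1.5 masks acuity testers and refractionists at outcome visits.

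It is also fair to say that the plan specifies only a similar analysis for the non-study eye. That this means change from baseline with baseline adjustment is an inference, though the natural one.

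**Conclusion.** The point holds as an internal contradiction: Protocol 2.3.2 item 3 is wrong as written against the schedule footnote. Its severity is minor.

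The effect is confined to the change-from-baseline and 5-letter-loss parts of the contralateral acuity analysis, for participants at sites that followed 2.3.2 literally. The number of such participants cannot be determined from the documents; it may be zero. No study-eye analysis, primary or secondary, is affected.

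The conclusion assumes that the contralateral acuity analysis follows the study-eye models, and that no procedure manual outside the documents has already resolved the conflict.

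**What to change.** Amend Protocol 2.3.2 item 3 to agree with the schedule footnote: E-ETDRS acuity with protocol refraction in both eyes at baseline.

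For participants already enrolled, report by arm the number of non-study eyes without a refracted baseline acuity, next to the contralateral acuity results. No separate exclusion rule is needed for eyes with no baseline score, since the ban on imputation already removes them from the change analyses.

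The cost is one line of protocol text and one row in a table. The amendment adds no procedure beyond what the schedule already requires.

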7.13 Protocol Adherence and Retention

1036 Protocol deviations and visit completion rates (excluding deaths) will be tabulated for each
1037 treatment group.
1038

7.14 Baseline Descriptive Statistics

1039 Baseline characteristics will be tabulated by treatment group and summary statistics appropriate
1040 to the distribution will be reported.
1041

1041 **7.15 Device Issues**

1042 Number of reported device issues will be tabulated by treatment group.

1043 **7.16 Planned Interim Analyses**

1044 There is no formal interim analysis planned for this study. The Data and Safety Monitory
1045 Committee (DSMC) will review tabulated safety and outcome data approximately every 6 months
1046 while the study is ongoing.

1047 **7.17 Subgroup Analyses**

1048 Subgroup analyses/assessments of effect modification (interaction) will be conducted for the
1049 primary outcome. Since there is no strong prior rationale for potential subgroup effects, these
1050 analyses will be considered exploratory and hypothesis generating, rather than definitive. It is
1051 recognized that the study is not powered to detect subgroup effects and that lack of significance is
1052 not necessarily an indication that subgroup effects do not exist. Additionally, interpretation of the
1053 analyses will depend on whether the primary analysis demonstrates a significant treatment group
1054 difference; in the absence of such a difference, subgroup analyses will be interpreted with caution.
1055 The general approach for these exploratory analyses will be to add an interaction term for the
1056 subgroup factor by treatment into the primary analysis model.

1057 Subgroup analyses will use observed data (no imputation) from participants who complete the
1058 primary outcome visit without missing CST data. Exploratory subgroup analysis will evaluate the
1059 effects of the following baseline factors:

- 1060 • Prior DME treatment: yes vs. no
- 1061 • Intravitreous treatment in non-study eye: recent (within 4 months) or planned
- 1062 • Lens status: phakic vs. pseudophakic
- 1063 • Baseline CST: continuous and categorical (dichotomized based on a clinically relevant cut
1064 point or an approximate median value)
- 1065 • Hemoglobin A1c: continuous and $<7.5\%$ vs. $\geq 7.5\%$
- 1066 • Iris color: blue, brown, or other

1067 Subgroup analyses will only be conducted if there are at least 20 eyes in each subgroup for each
1068 treatment group. There are no data to suggest that the treatment effect will vary by sex or
1069 race/ethnicity. However, both of these factors will be evaluated in exploratory subgroup analyses
1070 as mandated by NIH guidelines. Subgroup factors will be analyzed as continuous/ordinal variables
1071 where possible.

1072 **7.18 Multiple Comparisons/Multiplicity**

1073 Due to the large number of outcomes evaluated, only $P < .05$ will be considered of interest and
1074 warranting further exploration. It is recognized that this does not completely control the Type I
1075 error rate. There will be no other adjustments made for multiple comparisons or multiple testing.

1076 **7.19 Additional Tabulations and Analyses**

1077 To evaluate the potential contralateral effect, visual acuity, OCT measurements, and treatment for
1078 DME in non-study eyes will be tabulated at primary outcome visit by the treatment group assigned
1079 to the study eye. These outcomes will be analyzed and presented similarly to the primary and
1080 secondary analyses as specified above for the study eyes, with the exception that no imputation
1081 will be performed for missing data.

1082 This pilot study is being conducted to determine whether the conduct of a pivotal trial has merit
1083 based on an anatomic outcome and to provide information on outcome measures needed to design
1084 a pivotal trial. If the results of this study support proceeding with a pivotal trial after evaluation of
1085 all the data and discussion within DRCR, information from this study will contribute to designing
1086 the pivotal trial. The standard deviation of the difference in visual acuity will be used in the sample
1087 size calculation of the pivotal trial. Patient compliance (for example, the proportion of enrolled
1088 participants that are randomized and the proportion of randomized participants who comply with
1089 the use of the study device post-randomization) will also aid in the design of the pivotal trial.

1090 **CHAPTER 8: DATA COLLECTION AND MONITORING**

1091 **8.1 Case Report Forms and Device Data**

1092 The main study data are collected through electronic case report forms (CRFs). Compliance data
1093 are collected via electronic device data files obtained from the study device. When data are directly
1094 collected in electronic case report forms, this will be considered the source data. Each participating
1095 site will maintain appropriate medical and research records for this trial, in compliance with ICH
1096 E6 and regulatory and institutional requirements for the protection of confidentiality of
1097 participants.

1098 **8.2 Study Records Retention**

1099 Study documents should be retained for a minimum of 3 years following the NIH grant cycle for
1100 which the last visit was completed (expected to be December 31, 2026) or 2 years after the last
1101 approval of a marketing application in an ICH region and until there are no pending or
1102 contemplated marketing applications in an ICH region or until at least 2 years have elapsed since
1103 the formal discontinuation of clinical development of the investigational product, whichever is
1104 later. These documents should be retained for a longer period, however, if required by local
1105 regulations. No records will be destroyed without the written consent of JCHR, if applicable. It
1106 is the responsibility of JCHR to inform the investigator when these documents no longer need to
1107 be retained.

1108 **8.3 Quality Assurance and Monitoring**

1109 Designated personnel from the Coordinating Center will be responsible for maintaining quality
1110 assurance (QA) and quality control (QC) systems to ensure that the clinical portion of the trial is
1111 conducted and data are generated, documented and reported in compliance with the protocol, Good
1112 Clinical Practice (GCP) and the applicable regulatory requirements. Adverse events will be
1113 prioritized for monitoring.

1114 A risk-based monitoring (RBM) plan will be developed and revised as needed during the course
1115 of the study, consistent with the FDA “Guidance for Industry Oversight of Clinical Investigations
1116 — A Risk-Based Approach to Monitoring” (August 2013). Study conduct and monitoring will
1117 conform with 21 Code of Federal Regulations (CFR) 812.

1118 The data of most importance for monitoring at the site are participant eligibility and adverse events.
1119 Therefore, the RBM plan will focus on these areas. As much as possible, remote monitoring will
1120 be performed in real-time with on-site monitoring performed to evaluate the verity and
1121 completeness of the key site data. Elements of the RBM may include:

- 1122 • Qualification assessment, training, and certification for sites and site personnel
- 1123 • Oversight of Institutional Review Board (IRB) coverage and informed consent procedures
- 1124 • Central (remote) data monitoring: validation of data entry, data edits/audit trail, protocol
1125 review of entered data and edits, statistical monitoring, study closeout
- 1126 • On-site monitoring (site visits): source data verification, site visit report
- 1127 • Device accountability
- 1128 • Communications with site staff

1129 • Patient retention and visit completion

1130 • Quality control reports

1131 • Management of noncompliance

1132 • Documenting monitoring activities

1133 • Adverse event reporting and monitoring

1134 Coordinating Center representatives or their designees may visit the study facilities at any time in
1135 order to maintain current and personal knowledge of the study through review of the records,
1136 comparison with source documents, observation and discussion of the conduct and progress of the
1137 study.

1138 **8.4 Protocol Deviations**

1139 A protocol deviation is any noncompliance with the clinical trial protocol, GCP, or procedure
1140 requirements. The noncompliance may be either on the part of the participant, the investigator, or
1141 the study site staff. As a result of deviations, corrective actions are to be developed by the site and
1142 implemented promptly.

1143 The site PI/study staff is responsible for knowing and adhering to their IRB requirements. Further
1144 details about the handling of protocol deviations will be included in the monitoring plan.

1145

1146

1147 **CHAPTER 9: ETHICS/PROTECTION OF HUMAN PARTICIPANTS**

1148 **9.1 Ethical Standard**

1149 The investigator will ensure that this study is conducted in full conformity with Regulations for
1150 the Protection of Human Participants of Research codified in 45 CFR Part 46, 21 CFR Part 50, 21
1151 CFR Part 56, and/or the ICH E6.

1152 **9.2 Institutional Review Boards**

1153 The protocol, informed consent form(s), recruitment materials, and all participant materials will
1154 be submitted to the IRB for review and approval. Approval of both the protocol and the consent
1155 form must be obtained before any participant is enrolled. Any amendment to the protocol will
1156 require review and approval by the IRB before the changes are implemented to the study. All
1157 changes to the consent form will be IRB approved; a determination will be made regarding whether
1158 previously consented participants need to be re-consented.

1159 **9.3 Informed Consent Process**

1160 **9.3.1 Consent Procedures and Documentation**

1161 Informed consent is a process that is initiated prior to the individual's agreeing to participate in the
1162 study and continues throughout the individual's study participation. Extensive discussion of risks
1163 and possible benefits of participation will be provided to the participants and their families.
1164 Consent forms will be IRB-approved, and the participant will be asked to read and review the
1165 document. The investigator will explain the research study to the participant and answer any
1166 questions that may arise. All participants will receive a verbal explanation in terms suited to their
1167 comprehension of the purposes, procedures, and potential risks of the study and of their rights as
1168 research participants. Participants will have the opportunity to carefully review the written consent
1169 form and ask questions prior to signing.

1170 The participants should have the opportunity to discuss the study with their family members and
1171 their personal physicians(s) or think about it prior to agreeing to participate. The participant will
1172 sign the informed consent document prior to any procedures being done specifically for the study.
1173 The participants may withdraw consent at any time throughout the course of the trial. A copy of
1174 the informed consent document will be given to the participants for their records. The rights and
1175 welfare of the participants will be protected by emphasizing to them that the quality of their
1176 medical care will not be adversely affected if they decline to participate in this study.

1177 **9.3.2 Participant and Data Confidentiality**

1178 Participant confidentiality is strictly held in trust by the participating investigators, their staff, and
1179 the JCHR and their agents. This confidentiality is extended to cover biological samples in addition
1180 to the clinical information relating to participants. Therefore, the study protocol, documentation,
1181 data, and all other information generated will be held in strict confidence. No information
1182 concerning the study, or the data will be released to any unauthorized third party without prior
1183 written approval of the JCHR.

1184 The study monitor, other authorized representatives of the JCHR, or representatives of the IRB
1185 may inspect all documents and records required to be maintained by the investigator, including but

1186 not limited to, and medical records (office, clinic, or hospital). The clinical study site will permit
1187 access to such records.

1188 The study participant's contact information will be securely stored at each clinical site for internal
1189 use during the study. At the end of the study, all records will continue to be kept in a secure
1190 location for as long a period as dictated by local IRB and Institutional regulations.

1191 Separately from any research data, the coordinating center for the study, the Jaeb Center for Health
1192 Research (JCHR) in Tampa, Florida, will be provided with participant contact information to aid
1193 in study retention efforts. Study participant's contact information will be securely stored and will
1194 be destroyed at the end of the study.

1195 Study participant research data, which is for purposes of statistical analysis and scientific reporting,
1196 will be transmitted to and stored at JCHR. This will be stored separately from the participant's
1197 contact or direct identifying information. For research purposes, individual participants and their
1198 research data will be identified by a unique study identification number. The study data entry and
1199 study management systems used by clinical sites and by JCHR research staff will be secured and
1200 password protected. At the end of the study, all study databases will be de-identified and archived
1201 at JCHR.

1202 To further protect the privacy of study participants, a Certificate of Confidentiality is available
1203 from the NIH. This certificate protects identifiable research information from forced disclosure.
1204 It allows the investigator and others who have access to research records to refuse to disclose
1205 identifying information on research participation in any civil, criminal, administrative, legislative,
1206 or other proceeding, whether at the federal, state, or local level. By protecting researchers and
1207 institutions from being compelled to disclose information that would identify research participants,
1208 Certificates of Confidentiality help achieve the research objectives and promote participation in
1209 studies by helping assure confidentiality and privacy to participants.

1210 **9.3.3 Future Use of Stored Data**

1211 Data collected for this study will be analyzed and stored at the Jaeb Center for Health Research.
1212 After the study is completed, the de-identified, archived data will be made publicly available, for
1213 use by other researchers including those outside of the study. Permission for future use of the data
1214 will be included in the informed consent.

1215

1216

CHAPTER 10: REFERENCES

